7.9. Study Endpoints

7.8.1 Primary Outcome

The primary outcome will be headache recurrence 48 hours after discharge. Headache recurrence will be defined as: for patients who were pain-free at ED discharge (ie. pain intensity of 0), any return of head pain (ie. pain intensity of 1 or greater) will be coded as a recurrence, and for patients who had persistent head pain at discharge, an increase in head pain since ED discharge will be coded as recurrence as well (ie. an increase in their score on the 4-point scale as compared to their score at ED discharge). Therefore, the primary outcome will involve the comparison of the proportion of patients with headache recurrence in each group within 48 hours of ED discharge. Although formal statistics on reliability and validity are unavailable, assessment of the primary outcome, as described above, is congruent with prior studies on the efficacy of dexamethasone for this indication in adults (24,29).

The rationale for using headache recurrence as the primary outcome is derived from evidence from adult studies that have established efficacy for dexamethasone in preventing migraine recurrence in the short-term(15–18), but found no apparent impact on acute pain relief in the ED setting(57). The rationale for measuring recurrence of headache at 48 hours is three-fold: 1) the International Headache Society guidelines for controlled trials of drugs in migraine(11) defines recurrence as "any headache pain from 2 to 48 hours after drug administration, regardless of its severity", 2) prior studies assessed the efficacy of steroids (including dexamethasone) in preventing migraine recurrence anywhere from 24 to 72 hours after treatment, with the 48 hour mark being used most commonly(20,22,24–26,29,58–60), 3) the half-life of dexamethasone in children and adolescents is somewhere between 2.33 and 9.54 hours(50), meaning that it is cleared from the body between 11.7 and 47.7

hours after ingestion (after 5 half-lives only 3.1% of the drug remains in the body).

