6.1. Inclusion Criteria

Patients will be eligible for the study if:

- 1. Between the ages of 8 and 18 years (ie. > 8.0 years and < 18.0 years)
- 2. Diagnosed with migraine according to a modified version of International Classification of Headache Disorders 3rd edition (ICHD-3, beta version, see Table 1) diagnostic criteria for pediatric migraine(52)

NB. The use of the International Classification of Headache Disorders for migraine diagnosis is the standard for trials assessing both acute and prophylactic medications for migraine, according to the 2012 International Headache Society guidelines for controlled trials of drugs in migraine ($3^{\rm rd}$

edition)(11). However, there has been controversy about the application of these criteria to trials in the ED and many ED trials have used other criteria for migraine diagnosis. Both an adult(53) and a pediatric study(54) have shown that the ICHD criteria lack sensitivity for migraine diagnosis in the ED. Criterion A, which establishes that patients must have had five headaches meeting ICHD migraine criteria, is particularly problematic in the ED setting for several reasons, one of which is that patients commonly present to the ED with their first migraine and will therefore not meet this criterion. It has been shown that removal of criterion A increases the sensitivity of the ICHD criteria in the ED setting(54,55). Hence, for the proposed study, criterion A will be modified to increase the sensitivity of the criteria: criterion A will only require that the current headache meet ICHD-3 (beta) criteria, as opposed the requirement for five headaches meeting criteria (see Table 1).

Table 1. International Classification of Headache Disorders 3^{rd} edition (beta version) criteria for pediatric migraine(52) and modified criteria for proposed study

Criterion	ICHD-3 (beta) Migraine Criteria	Modified Criteria for Proposed Study		
A	At least 5 attacks fulfilling criteria B-D	Present attack fulfilling criteria B-D		
В	Attacks last 2-72 hours if untreated or unsuccessfully treated	 Attack lasting 2-72 hours if untreated or unsuccessfully treated 		

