7.8.2 Secondary Outcomes

Several secondary outcomes are of interest:

- 1. Pain intensity will be assessed at baseline, 2 hours after having received the study intervention (or at the time of ED discharge if prior to 2 hours) and at the time of ED discharge. As is suggested in the International Headache Society guidelines for controlled trials of drugs in migraine(11), pain intensity will be measured using a 4-point scale where 0=no headache, 1=mild headache, 2=moderate headache and 3=severe headache.
- 2. Persistent pain freedom, defined as the proportion of patients in each group who achieved pain freedom at 2 hours (or at the time of ED discharge if prior to 2 hours) and were free of pain without the use of rescue medication at 48 hours(11), will be assessed.
- 3. Patient satisfaction will be assessed at discharge and again at follow-up with the following 5-point Likert scale: 5=very satisfied, 4=satisfied, 3=neutral, 2=unsatisfied, 1=very unsatisfied.
- 4. The proportion of patients in each group with recurrence within the 7 days following ED discharge will be assessed. The 7 day time point was selected based on its use in a previous study(29) and given our interest in exploring potential longer treatment effects of dexamethasone for this indication.
- 5. The number of patients with return ED visits within 7 days of ED discharge will be assessed through chart review.
- 6. Adverse events will also be queried at 2 hours (or at the time of ED discharge if prior to 2 hours), at discharge and in the follow-up questionnaires.

8. Expected Duration of Participant Participation

Participants will remain in the ED for variable lengths of time depending on the time required for the acute pain interventions to alleviate the migraine pain. It is anticipated that participants will remain in the ED for 1.5-6 hours on average. Participants will also be asked to complete two electronic or telephone follow-up questionnaires, which are expected to last a maximum of 5 minutes per follow-up. Participation in the study will end after the second follow-up electronic or telephone questionnaire, that is, 7 days following discharge.

9. Study Medication

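### In patients discharged with mild or moderate pain, a headache that clears at home and returns no higher than the discharge score is coded as no recurrence

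*Combined protocol and SAP*

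**What the plan says.** Section 7.8.1 Primary Outcome (placed under 7.9 Study Endpoints) defines recurrence in two branches. For patients at 0 at discharge, "any return of head pain (ie. pain intensity of 1 or greater) will be coded as a recurrence". For the rest, "for patients who had persistent head pain at discharge, an increase in head pain since ED discharge will be coded as recurrence as well", which the text then spells out as "an increase in their score on the 4-point scale as compared to their score at ED discharge". The scale is the "4-point scale where 0=no headache, 1=mild headache, 2=moderate headache and 3=severe headache".

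The section says that formal reliability and validity figures are not available for this assessment, and defends it on the ground that it "is congruent with prior studies on the efficacy of dexamethasone for this indication in adults".

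Section 7.8.2, item 4, adds the later time point: "The proportion of patients in each group with recurrence within the 7 days following ED discharge will be assessed". It gives no separate definition of recurrence. Criterion B of the modified diagnostic criteria (section 6.1, Table 1) describes an eligible attack as "Attack lasting 2-72 hours if untreated or unsuccessfully treated".

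The fifth aim in section 5.1 is to estimate, by group, the proportion with recurrence within 48 hours. Section 10.1 says the pilot data are to inform a large multicentre trial. Section 10.2 plans Fisher's exact test and a relative risk with a 95% confidence interval.

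**The concern.** The second branch keeps the discharge score as the reference for the whole window, even when the headache that produced it has ended. Take two children. One leaves pain-free and has mild pain (1) at 30 hours: recurrence. The other leaves with moderate pain (2), is pain-free that evening, and has moderate pain (2) again at 30 hours: no recurrence, because 2 is not higher than 2. The second child has relapsed, and with worse pain than the first.

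In a pilot of 20 the p-value is not what is at stake. The group proportions are a stated product of the study and are meant to be carried into the main trial. Recruiting more patients would not correct an under-count that comes from the definition, and the definition itself is likely to be carried forward.

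**Working it through.** 1. Apply the rule to every path in which pain clears to 0 after discharge and then returns. A discharge score of 0 needs a return of 1 or more; a discharge score above 0 needs a return higher than that score.

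| Discharge score | Returns at 1 | Returns at 2 | Returns at 3 |
|---|---|---|---|
| 0 | counted | counted | counted |
| 1 (mild) | not counted | counted | counted |
| 2 (moderate) | not counted | not counted | counted |

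For discharge at 1 or 2 there are 2 × 3 = 6 paths. Three are not counted: 1→0→1, 2→0→1 and 2→0→2. These are paths, not frequencies; 3 of 6 does not mean half of the relapses. (Discharge at 3 is a separate matter of the scale ceiling: no later score can exceed 3.)

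2. Check whether the wording allows another reading. The phrase about an increase since discharge could, taken alone, cover a rise from a low point reached at home. The explanatory clause "an increase in their score on the 4-point scale as compared to their score at ED discharge" closes that reading.

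3. Check the 7-day outcome. Item 4 of section 7.8.2 does not redefine recurrence, so the only definition available is that of 7.8.1. With attacks of 2 to 72 hours (3 days) under criterion B, the index attack would normally be over by days 4 to 7. A new moderate attack on day 5 in a child discharged at 2 is still not counted.

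4. Check whether another endpoint recovers these events. Persistent pain freedom (7.8.2, item 2) requires pain freedom at 2 hours, or at discharge if earlier, and does not separate relapse from continuing pain. Return visits (item 5) capture only those who come back to the ED.

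5. Work out which measures are affected. Let f be the share of true relapses that occur in patients discharged with pain, and m the share of those that return no higher than the discharge score. The share counted is s = 1 − f × m. If s is the same in both arms:
- each observed proportion is s × p;
- the observed difference is s × (p1 − p2);
- the observed relative risk is (s × p2)/(s × p1) = p2/p1, unchanged.

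6. Illustrate. The documents give neither f nor m, so both are assumed at 25%, 50% and 75%. The starting rates are the adult oral-dexamethasone counts in section 4, Figure 1: placebo 38/113 = 33.6%, dexamethasone 28/121 = 23.1%. As a check on those counts, the Mantel-Haenszel odds ratio recomputed from the two trials is 0.598 (0.336 to 1.064), which matches the stated 0.60 (0.34 to 1.06). The last column is the two-proportion sample size with pooled variance under the null, two-sided 0.05, 1:1, at an assumed 80% power.

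| f = m | s | Placebo | Dexamethasone | Difference | Relative risk | N per arm |
|---|---|---|---|---|---|---|
| full capture | 1 | 33.6% | 23.1% | 10.5 points | 0.69 | 289 |
| 25% | 0.94 | 31.5% | 21.7% | 9.8 points | 0.69 | 316 |
| 50% | 0.75 | 25.2% | 17.4% | 7.9 points | 0.69 | 424 |
| 75% | 0.44 | 14.7% | 10.1% | 4.6 points | 0.69 | 810 |

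The table shows direction and mechanism only. It treats the adult rates as complete capture, which the documents do not establish.

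**The case against.** The strongest reply is that the rule is deliberate. The section writes a separate branch for residual pain, is open about the lack of validation, and follows two adult trials. This stands as an argument for comparability, and it is why the current definition should still be reported. It does not make a headache that ended and came back a non-recurrence.

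A second reply is that the planned effect measure is the relative risk, which equal under-capture leaves alone. That is correct. A reader might infer that the rule dilutes the treatment comparison in general; the documents support this only for the proportions and the absolute difference.

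A third is that the follow-up form (Appendix C) is not in the text available, and Table 2 lists assessment of headache recurrence separately from pain intensity at both follow-ups. The form may therefore already ask whether the headache came back. Even so, the coding rule as written would set that answer aside.

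Other stronger readings also fail. A reader might say that the cited guideline definition, "any headache pain from 2 to 48 hours after drug administration, regardless of its severity", contradicts the rule. The section cites it to justify the 48-hour time point; it cannot reach a day-5 attack, and read literally it would also count pain that never cleared. A reader might say that relapses are missed in everyone discharged with pain; step 1 shows that a return above the discharge score is counted.

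The last objection concerns the remedy. It relies on recall of a pain-free interval over up to 7 days, and fluctuating pain could be taken for relapse. That is a real cost.

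**Conclusion.** The concern holds as a gap in the endpoint definition and should be corrected. For patients discharged at 1 or 2, complete clearance followed by return at or below the discharge score is coded as no recurrence at 48 hours and, because no other definition is given, at 7 days. The group proportions needed for the fifth aim, and the absolute difference, may be understated.

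The size cannot be stated. A reader might assume that 30% to 60% leave with a score of 1 or 2, apply the one-week relapse range of 26% to 68% from section 4, suppose that half return no higher than at discharge, and obtain 0.30 × 0.26 × 0.5 = 3.9 to 0.60 × 0.68 × 0.5 = 20.4 percentage points. The first and last inputs have no source, and the relapse range is for paediatric ED migraine patients generally, not for those discharged in pain whose headache then cleared. Nor can the pooled adult difference of 10 points be treated as a true value that this rule would shrink, since it may already reflect a similar definition.

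Equal loss in both arms is itself an assumption. Section 7.8.1 notes no apparent effect of dexamethasone on acute ED pain relief in adults, which makes it plausible. If treatment did change pain at discharge, the arms would differ in their chance of being coded, and the comparison could shift in either direction.

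**What to change.** In section 7.8.1, and for item 4 of section 7.8.2, define recurrence in patients with pain at discharge as either an increase over the discharge score, or any return of head pain (score 1 or more) after the headache has gone away completely (score 0) following discharge. State in item 4 that this definition applies at 7 days.

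Ensure that both follow-up questionnaires ask whether the headache went away completely after leaving the ED and whether it came back, adding the question if Appendix C lacks it. Report the proportions under the current wording alongside.

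The cost is one clause in two definitions and at most one question in two existing questionnaires, with no change to visits or sample size. The price is reliance on recall of a pain-free interval and slightly less direct comparability with the adult trials. Reporting both definitions preserves that comparability and shows how far the results depend on the recalled interval.

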7.8.2 Secondary Outcomes

Several secondary outcomes are of interest:

- 1. Pain intensity will be assessed at baseline, 2 hours after having received the study intervention (or at the time of ED discharge if prior to 2 hours) and at the time of ED discharge. As is suggested in the International Headache Society guidelines for controlled trials of drugs in migraine(11), pain intensity will be measured using a 4-point scale where 0=no headache, 1=mild headache, 2=moderate headache and 3=severe headache.
- 2. Persistent pain freedom, defined as the proportion of patients in each group who achieved pain freedom at 2 hours (or at the time of ED discharge if prior to 2 hours) and were free of pain without the use of rescue medication at 48 hours(11), will be assessed.
- 3. Patient satisfaction will be assessed at discharge and again at follow-up with the following 5-point Likert scale: 5=very satisfied, 4=satisfied, 3=neutral, 2=unsatisfied, 1=very unsatisfied.
- 4. The proportion of patients in each group with recurrence within the 7 days following ED discharge will be assessed. The 7 day time point was selected based on its use in a previous study(29) and given our interest in exploring potential longer treatment effects of dexamethasone for this indication.
- 5. The number of patients with return ED visits within 7 days of ED discharge will be assessed through chart review.
- 6. Adverse events will also be queried at 2 hours (or at the time of ED discharge if prior to 2 hours), at discharge and in the follow-up questionnaires.

8. Expected Duration of Participant Participation

Participants will remain in the ED for variable lengths of time depending on the time required for the acute pain interventions to alleviate the migraine pain. It is anticipated that participants will remain in the ED for 1.5-6 hours on average. Participants will also be asked to complete two electronic or telephone follow-up questionnaires, which are expected to last a maximum of 5 minutes per follow-up. Participation in the study will end after the second follow-up electronic or telephone questionnaire, that is, 7 days following discharge.

9. Study Medication

9.1 Study Medication Description

The study intervention will consist of an oral compound of dexamethasone, given orally at a one time dose of 0.6mg/kg to a maximum of 15mg. The dexamethasone will be compounded at the CHEO research pharmacy using a combination of dexamethasone sodium phosphate USP injection 10mg/mL (PRDexamethasone Omega Unidose; see product monograph) manufactured by Omega Laboratories Ltd. and Ora-Blend®, a flavored oral suspending vehicle manufactured by Galenova Inc. The compound is created by combining 10mL of the dexamethasone 10mg/mL sodium phosphate USP and 90mL of Ora-Blend®. The final oral suspension has a concentration of 1mg/mL of dexamethasone and a pinkish hue with a milky consistency. The appropriate dose for the participant will be drawn up into an oral syringe, which will be labeled for investigational use. The commercial label will not be present given that this study is blinded.

9.2 Placebo Description

The placebo will comprise Ora-Blend®, a flavored oral suspending vehicle manufactured by Galenova Inc. Participants randomized to the placebo group will be given Ora-Blend® 0.6mL/kg for a maximum of 15mL. Ora-Blend® has a pinkish hue and a milky consistency. The appropriate volume for the participant will be drawn up into an oral syringe, which will be labeled for investigational use. The commercial label will not be present given that this study is blinded.

9.3 Accountability Procedures and Storing

The dexamethasone oral suspension will be stored in the Pharmacy Department in amber plastic bottles at room temperature, between 20°C and 25°C. The Ora-Blend placebo suspension will also be stored in the Pharmacy Department, in white opaque bottles at room temperature, between 20°C and 25°C. The compound maintains stability for 91 days(61,62) and the vials will be labeled with the expiration date. After the expiration date, remaining vials will be destroyed in compliance with the Pharmacy Department's standard operating procedures (SOP) for the destruction of investigational drugs, which are compliant with the guidelines as set out in ICH(51).

The dexamethasone and placebo vial labeling will be compliant with Health Canada Division 5 Food and Drug Regulation clinical trial labeling guidelines (see Figures 4 and 5 for labels).

Figure 4. Labels for dexamethasone vials

Dexamethasone Dexamethasone 1mg/mL oral suspension- X mL Suspension 1mg/mL orale- X mL Expiration: DD-MMM-YYYY Expiration: DD-MM-YYYY Store at room temperature +20°C and +25°C. Conserver à temperature ambiente entre +20°C and protected from light in amber plastic bottles +25°C, à l'abri de la lumière dans des bouteilles en Lot # ----plastique couleur ambre et opaques Protocol Code: -----Lot # -----Sponsor: Children's Hospital of Eastern Ontario, 401 Code du Protocole: -----[name] Commenditaire: Centre Hospitalier Pour Enfants de L'Est de L'Ontario, [name], Investigational drug to be used only by a qualified Investigator [name] Médicament expérimental à être utilisé seulement par un Investigateur qualifié

Figure 5. Labels for placebo vials

Placebo (Ora-Blend®) Placebo (Ora-Blend®) 1mg/mL oral suspension- X mL Suspension 1mg/mL orale Expiration: DD-MMM-YYYY Expiration: DD-MM-YYYY Store at room temperature +20°C and +25°C, Conserver à temperature ambiente entre +20°C and protected from light in white opaque bottles +25°C, à l'abri de la lumière dans des bouteilles Lot # ---blanches et opaques Protocol Code: ---Lot # ---Sponsor: Children's Hospital of Eastern Ontario, Code du Protocole: -----[name] Commenditaire: Centre Hospitalier Pour Enfants de Investigational drug to be used only by a qualified L'Est de L'Ontario, [name], Investigator [name] Médicament expérimental à être utilisé seulement par un Investigateur qualifié

When a patient is randomized to the study, pre-printed orders with the participant's identification number (corresponding to the randomization code, see above), and their identifying information (ie. name, hospital identification number, etc) will be sent to the Pharmacy. The research pharmacist will then check the randomization scheme and prepare the appropriate intervention, either dexamethasone or placebo, according to the participant's identification number/randomization code. At this time, the patient's identifying information will be entered into the research pharmacy's password-protected group assignment list along with their study identification number and assigned intervention, so that this data is recorded in case unblinding is required for safety reasons.

The study intervention will be drawn into a syringe, which will be capped and labeled in compliance with Health Canada Division 5 Food and Drug Regulation clinical trial labeling guidelines and the guidelines of the Ontario College of Pharmacists. Once the syringe is filled, capped, and labeled, a research pharmacist or technologist will bring it to the ED and deliver it to the treating nurse.

Syringes that are not administered to patients will be sent back to the Pharmacy Department for destruction according to the Pharmacy's SOPs for destruction of investigational products.

Drug accountability forms will be completed and stored in the Pharmacy and records will be maintained in accordance with Health Canada Division 5 Food and Drug Regulation guidelines.

9.4 Monitoring for Subject Compliance

Given that this study will involve a one time oral dose of either dexamethasone or placebo given in the ED, no compliance issues are anticipated. Loss to follow-up will likely occur. Given that this is a pilot randomized controlled trial, monitoring of the rate of loss to follow-up is one of the goals of the study.

10. Statistical Procedures

10.1 Sample Size

As described above, the proposed study will be a pilot study. The goal will eventually be to use this pilot data to inform the design and implementation of a large, multi-center trial on the efficacy of dexamethasone for preventing migraine recurrence in the pediatric ED. For the purposes of the proposed pilot study, 20 patients will be recruited. The recruitment period will be over 6 months. The CHEO ED has over 300 migraine visits per year, and 6 months is thus expected to be a sufficiently long period to capture 20 eligible migraine patients.

